#### 4.1. Protocol Deviations

Important protocol deviations (including deviations related to eligibility criteria, conduct of the trial, patient management or patient assessment) will be summarised and listed.

Exclusions from the main study populations described above will also be summarised. (Please refer to [Appendix 1: Protocol Deviation Management and Definitions for Per Protocol Population](#)).

Protocol deviations will be tracked by the study team throughout the conduct of the study in accordance with the Protocol Deviation Management Plan [31OCT2019, Version 3.0] using the Protocol Deviation Management System (PDMS)

- Data will be reviewed prior to unblinding and freezing the database to ensure all important deviations and deviations which may lead to exclusion from the analysis are captured. Protocol deviations related to incorrect treatment will be managed as described below.
- This dataset will be the basis for the summaries and listings of protocol deviations.

A separate summary and listing of all eligibility criteria deviations will also be provided. This summary will be based on data as recorded on the eligibility page of the eCRF.

Handling of recording of treatment dispensing errors as protocol deviation:

- Dispensing of incorrect container will be logged as an important PD and included in the PD dataset.
- If it is recorded that the incorrect container was dispensed, it will NOT be flagged as a reason for exclusion from the Per Protocol population, since it is not known

**CONFIDENTIAL**

204837

- before DBF/Unblinding if the incorrect container contained the incorrect treatment.
- Decisions on whether or not the participant took incorrect treatment because of treatment dispensing errors have to be made after unblinding (i.e. post DBF). For Daprodustat/Placebo, this can be done after unblinding using the corresponding container number. For rhEPO/saline, to which no container numbers are assigned, if the incorrect treatment was given, it would be reported as an unblinded protocol deviation in the PDMS and be entered into the unblinded eCRF, which is designed specifically for capturing the wrong rhEPO dose.

## 5. CONSIDERATIONS FOR DATA ANALYSES AND DATA HANDLING CONVENTIONS

### 5.1. Study Treatment & Sub-group Display Descriptors

Treatment Group Descriptions			
PPD Randomization System		Data Displays for Reporting	
Code	Description	Description	Order in TLF
1	daprodustat	Dapro	1
2	rhEPO	rhEPO	2
		Total	3

NOTE: “No Treatment” and “All Treated” will be included in selected tables, when needed, and will be displayed in the order shown in the table shell.

Treatment comparisons will be displayed as follows using the descriptors as specified:

1. daprodustat vs rhEPO

### 5.2. Baseline Definitions and Derivations

#### 5.2.1. Baseline Definitions

For all endpoints (except as noted in baseline definitions) the baseline value will be the latest non-missing pre-dose assessment on or before the randomization date, including those from unscheduled visits. If time is not collected, Day 1 assessments are assumed to be taken prior to first dose and used as baseline (except as noted in the baseline definitions for post-dialysis SBP, DBP, MAP, HR and weight).

Parameter	Study Assessments Intended as Baseline		Baseline Used in Data Display
	Screening (Week -4)	Day 1 (Pre-Dose)	
Efficacy			
Hgb		X	Day 1
Monthly IV iron 		X	Day 1
Iron parameters		X	Day 1
Safety			
Pre-dialysis SBP, DBP, MAP, HR, Weight		X	Day 1
Estimated dry weight		X	Day 1
Post-dialysis  SBP, DBP, MAP, HR, Weight	X		Week -4
Lipid parameters, clinical chemistry,		X	Day 1

## CONFIDENTIAL

204837

Parameter	Study Assessments Intended as Baseline		Baseline Used in Data Display
	Screening (Week -4)	Day 1 (Pre-Dose)	
hematology, other laboratory and hepatobiliary (liver) tests			
ECG 	X		Week -4
PRO			
PGI-S		X	Day 1

NOTE: Unless otherwise stated, the mean of replicate assessments at any given time point will be used as the value for that time point.

[1]: Baseline monthly IV iron dose will be defined as total IV iron (mg) over the 12 weeks prior to randomization. See Section 14.6.3.

[2]: Post-dialysis baseline values for SBP, DBP, MAP, HR, and weight will be defined as the latest non-missing pre-dose assessment before the randomization date. This will most often be the value recorded at the Week -4 visit. However, for cases where the treatment start date falls after the randomization date, the randomization date will be used as the baseline measurement.

[3]: The Week -4 (screening) ECG must be performed pre-dialysis, and may be performed on any dialysis day from the Week -4 visit to the Day 1 visit, except during the first dialysis session of the week. Two additional ECGs are required if the screening ECG indicates prolonged QTc. In this case, the average QTcB value of all three ECGs will be used as the baseline QTcB.

### 5.2.2. Derivations and Handling of Missing Baseline Data

Unless otherwise stated, if baseline data is missing no derivation will be performed and baseline will be set to missing.

#### *Change from Baseline*

Definition	Reporting Details
Change from Baseline	= Post-Dose Visit Value – Baseline

#### NOTES:

- Unless otherwise specified, the baseline definitions specified in Section 5.2.1 Baseline Definitions will be used for derivations for endpoints / parameters and indicated on summaries and listings.
- Unless otherwise stated, if baseline data is missing no derivation will be performed and the change from baseline value will be set to missing.
- The baseline definition will be footnoted on all change from baseline displays.

#### *Percent Change from Baseline*

Lipid parameters will be log-transformed and the percent change from baseline will be reported. Other endpoints may also be log-transformed if deemed appropriate.

To calculate a geometric mean for baseline measurement or at a specified timepoint, the following steps are used:

1. Log-transform the data points
2. Calculate the mean and standard error (SE) of the log-transformed data

**CONFIDENTIAL**

204837

3. Exponentiate the mean, (if required, the mean – SE, mean + SE) and the endpoints of the confidence interval back to the original scale in order to obtain the geometric mean, (the geometric mean – SE, the geometric mean + SE) and the confidence interval for the geometric mean.
4. Coefficient of variation will be calculated as

$$CV = \sqrt{\exp(\text{Var}_{\log scale}) - 1} \times 100\%$$

To calculate a geometric mean for the ratio of a specific timepoint to baseline (expressed as a percent change from baseline), the following steps are used:

1. Log-transform the data at both the baseline and the specified timepoint
2. For each subject, calculate a change from baseline using the log-transformed data
3. Calculate the mean and standard error (SE) of the log-transformed data
4. Exponentiate the mean, (if required, the mean – SE, the mean + SE) and the endpoints of the confidence interval, back to the original scale and then subtract 1, then multiply everything by 100% in order to express the geometric mean, (the geometric mean – SE, the geometric mean + SE) and the confidence interval (CI) as the percent change from baseline.

So, geometric mean for percent change from baseline =

$$[ \text{Exp}(\sum \{ \log(\text{value at specified time point}_i) - \log(\text{baseline value}_i) \} / n) - 1 ] \times 100,$$

Where  $i$  = subject,  $n$  = total number of subjects, and  $\sum$  represents the sum over all subjects.

To calculate the minimum, median and maximum for the ratio of a specific timepoint to baseline (expressed as a percent change from baseline), the following steps are used:

1. Log-transform the data at both the baseline and the specified timepoint
2. For each subject, calculate a change from baseline using the log-transformed data
3. Calculate the minimum (median and maximum) of change from baseline using the log transformed data.
4. Exponentiate the minimum (median and maximum), back to the original scale and then subtract 1, then multiply everything by 100% in order to express the minimum (median and maximum) as the percent change from baseline.

So, minimum percent change from baseline =

$$[ \text{Exp}(\min \{ \log(\text{value at specified time point}_i) - \log(\text{baseline value}_i) \}) - 1 ] \times 100,$$

Where  $i$  = subject.

Unless otherwise specified, the baseline definitions specified in Section 5.2.1 will be used for derivations for endpoints/parameters and indicated on summaries and listings. Unless otherwise specified, if baseline data is missing, no derivation will be performed and the % change from baseline value will be set to missing. The baseline definition will be footnoted on all change from baseline displays.

### 5.3. Multicentre Studies

In this multicentre global study, enrolment will be presented by investigative site, country, and the regions.

Region	Countries
Region 1: Asia Pacific	Republic of Korea
Region 2: Eastern Europe	Poland, Romania, Russian Federation
Region 3: Western Europe/Canada/Australia	Australia, Canada, France, Italy, Spain, United Kingdom
Region 4: Latin America	Argentina, Brazil
Region:5: USA	USA

For any summaries that include information related to a subject's center or investigator, the most recent center and investigator at the time that the database is final will be used.

### 5.4. Examination of Covariates, Other Strata and Subgroups

#### 5.4.1. Covariates and Other Strata

The list of covariates and other strata may be used in descriptive summaries and statistical analyses, some of which may also be used for subgroup analyses. Additional covariates and other strata of clinical interest may also be considered.

Category	Details
Strata	Regions listed in Section 5.3.
Covariates	Baseline Hgb (For the analysis of the primary endpoint and other analyses of Hgb-related endpoints)  For subgroup analyses, statistical models will be adjusted for the covariates used in the original analysis (randomization stratification factor and baseline hemoglobin), subgroup, treatment and treatment by subgroup interaction (see Section 5.4.2 for the subgroup variables.).

Randomization is stratified by the prognostic factor, region, which will be taken into account within the analysis models.

#### 5.4.2. Examination of Subgroups

- The following is a non-exhaustive list of covariates that may be used in summaries of demographics, descriptive summaries and statistical analyses.
- Additional covariates of clinical interest may also be considered.
- If the percentage of subjects is small within a particular subgroup, then the subgroup categories may be refined prior to unblinding the trial.

**CONFIDENTIAL**

204837

- If the category cannot be refined further, then descriptive rather than statistical comparisons may be performed for the particular subgroup. If there are less than 25 subjects in one of the subgroup categories with two levels (e.g., history of stroke (Yes/No)), then statistical comparison will not be performed for that subgroup. Due to small sample sizes in American Indian or Alaskan Native, Native Hawaiian or Other Pacific Islander, and Mixed Race categories, statistical comparison for race group will include Asian, Black or African American, and White categories only. For baseline Hgb subgroup, if there are fewer than 25 subjects in the category  $<9$  g/dL, the categories  $<9$  g/dL and  $9 - <10$  g/dL will be combined to  $< 10$  g/dL.
- A pre-specified strategy for prioritizing subgroups/covariates is defined below (as recommended in the 2015 draft Committee for Medicinal Products for Human Use (CHMP) guidance on the investigation of subgroups in confirmatory clinical trials)
- The primary and principal secondary endpoints will be evaluated for the subgroups below. Although subgroup analyses are aimed to assess for consistency with the overall results, they may have low power, especially if the subgroup is small or has a low number of events. Statistical models (ANCOVA) will be adjusted for the covariates used in the original analysis, subgroup, treatment and treatment by subgroup interaction. For the subgroup Regions combined (USA vs. non-USA), the randomization stratification factor Region (with 5 levels, Regions 1- 5) will not be included in the statistical model.
- For subgroup analyses of time-to-event endpoints, point estimates and confidence intervals for the rate per 100 person-years will be reported for each treatment group within a subgroup, as well as the point estimate and two-sided 95% CI for the difference in rates between treatments within a subgroup. For within-group rates, the two-sided 95% CI will be obtained using an exact Poisson method. For difference in rates between treatments, the two-sided 95% CI will be constructed with a Normal approximation using Wald's method [Liu, 2006].
- For Hgb using mixed model repeated measures (MMRM) approach in the original analysis, the statistical model for the corresponding subgroup analyses will have the following factors: region, baseline value, baseline value by time, and subgroup by treatment by time interaction terms. The model will be run without main effects (treatment, visit, and subgroup) and two-way interaction terms (subgroup by time, treatment by time, and subgroup by treatment) for computational ease since in SAS, the main effects and two-way interaction terms are included within the three-way interaction term, thus giving equivalent result. If the model encounters convergence issues, then the following steps will be performed in this sequence:
  - Step 1: Use Fisher scoring method
    - Scoring=0 will be used as the first option, which is equivalent to no scoring, and if the model fails to converge, the scoring will be updated to scoring=1
    - The scoring will be updated each time the model fails to converge until a maximum of scoring=4 is reached. At this point, if the model fails to converge, Step 2 will be utilized.

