**CONFIDENTIAL**

204837

- Step 2: If the model fails to converge, instead of unstructured, TOEPH variance-covariance matrix will be used in conjunction with Step 1
- Step 3: If the model fails to converge, denominator degrees of freedom will be changed from Kenward-Roger to Residual in conjunction with Steps 1 and 2.

Please note that if the model still fails to converge after Step 3, model-adjusted subgroup analysis will not be performed. The associated descriptive statistics will be displayed. If the original model fails to converge, but it converges after one of the three steps, the output will display the changes made to the original model in a footnote.

- When a subgroup category assesses the same or a similar parameter (e.g., country is similar to region) as the prognostic stratification variable, the randomization stratification variable will be removed from the model.
- Point estimates and two-sided 95% CIs will be estimated within subgroups, the subgroup by treatment interaction p-value will be calculated and subgroup results will be graphically presented (e.g. Forest Plots). Directional consistency in subgroup treatment effects and a non-significant interaction p-value (two-sided 10% level) would support that the overall treatment effect is broadly applicable to the full study population. Subgroup analyses will not be adjusted for multiplicity.
- In addition, a nominal one-sided non-inferiority p-value using a non-inferiority margin of -0.75 g/dL and a nominal one-sided superiority p-value will be generated for the difference between treatment groups for each level of the hyporesponder subgroup analyses of the primary Hgb endpoint.

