
 
For the secondary analysis of Hgb change from baseline to Week 52, a mixed model repeated measures (MMRM) approach will be used with an unstructured covariance matrix to compare the difference in means between arms. The model will be fitted to Hgb data collected after baseline up to Week 52, excluding values collected during the stabilization period (Day 1 to Week 28). The model will include factors for treatment, time, prognostic randomization stratification factor (region, see Section 5.3), baseline Hgb and the baseline Hgb by time and treatment by time interaction terms. Analyses will be done with the MIXED procedure in SAS, using the Kenward-Roger option to estimate denominator degrees of freedom and standard errors. This analysis will be performed using all available Hgb values (on and off-treatment) and separately using evaluable Hgb values only (see Section 14.6.3). In the analysis using all available Hgb values, subjects who withdraw from the study before Week 52 are considered to be missing at random and in the analysis using evaluable Hgb values, subjects who permanently discontinue study treatment before Week 52 are assumed to be missing at random.
 
For the analysis of % time in range, the method by Rosendaal [Rosendaal, 1993] will be used to calculate the percentage of time (days) a subject's Hgb is below, within and above the Hgb analysis range of 10 to 11.5 g/dL during the EP (Weeks 28-52). A van Elteren test (stratified Wilcoxon rank sum test) will be used to compare the percentage of time in range between treatment arms, adjusting for treatment and the prognostic randomization stratification factor (see Section 5.3). This analysis will be performed using evaluable Hgb
 

values only. Hodges-Lehmann estimate of the treatment difference will be used to assess non-inferiority in % time in range.
 
 
For the Hgb responder analysis, mean Hgb during the EP will be defined as in the while on-treatment evaluable Hgb supportive analysis (Section 14.6.3). Responders will be subjects with a mean Hgb during the EP that falls within the Hgb analysis range of 10-11.5 g/dL. A Cochran-Mantel-Haenszel (CMH) chi-squared test, adjusting for treatment and the prognostic randomization stratification factor (region as randomized, see Section 5.3), will be used to compare the number and % of responders between the treatment groups.
 

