
 
Subgroup analyses will be performed for all Hgb variability endpoints, using the region and hyporesponder subgroups only (described in Section 5.3 & Section 5.4), in a method similar to that described for the subgroup analyses of the primary and principal secondary analyses
 

CONFIDENTIAL

204837

*Time to Rescue*

Secondary Efficacy Statistical Analyses: Time to Rescue
Endpoint / Variables

 
Time to stopping study treatment due to meeting rescue criteria
 

Model Specification

 
The Cox Proportional Hazards model will adjust for the following baseline categorical values: 
 
Treatment
 
Region (as randomized, see Section 5.3 & Section 5.4.1)
 
 
 
Confidence intervals for the rate per 100 person-years will also be reported. For within-group rates, the two-sided 95% CI will be obtained using an exact Poisson method. For difference in rates between treatments, the two-sided 95% CI will be constructed with a Normal approximation using Wald's method [Liu, 2006].
 
Analysis will include only those efficacy endpoints occurring within the time period for treatment discontinuation. Calculation of time-to-event or censoring is described in further detail in Section 14.6.3.
 
Time to stopping study medication due to meeting rescue criteria is defined as the time from Randomization until the date on which a subject permanently stops study medication due to meeting criteria for rescue.
 

Model Results Presentation

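### The MMRM subgroup model keeps only the three-way term, and the SAP does not say which test gives the subgroup-by-treatment p-value (minor)

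*SAP*

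**What the plan says.** SAP 7.3.1 (Hgb Variability) analyses one secondary endpoint with repeated measures: "For the secondary analysis of Hgb change from baseline to Week 52, a mixed model repeated measures (MMRM) approach will be used". Values from the stabilization period are left out, so the model covers Weeks 28 to 52, which SAP 7.1.5.1 counts as seven scheduled visits. The same section plans subgroup versions "using the region and hyporesponder subgroups only".

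SAP 5.4.2 gives the subgroup model. Its terms are "region, baseline value, baseline value by time, and subgroup by treatment by time interaction terms". It adds: "The model will be run without main effects (treatment, visit, and subgroup) and two-way interaction terms". The reason offered is ease of computation, with the assurance that "the main effects and two-way interaction terms are included within the three-way interaction term, thus giving equivalent result".

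The same section then applies a common rule to subgroup analyses: "the subgroup by treatment interaction p-value will be calculated and subgroup results will be graphically presented". On reading that p-value it says that "a non-significant interaction p-value (two-sided 10% level) would support that the overall treatment effect is broadly applicable" to the full study population. It does not say which test, contrast or visit supplies the p-value in the MMRM case.

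**The concern.** An interaction p-value is usually read from the subgroup-by-treatment line of the model output. Here that term has been removed. The only model term left that involves both subgroup and treatment is the three-way one, and the SAP describes the reduced model as equivalent without limiting the word to estimates.

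In a model with no lower-order terms, the test of the three-way term asks whether all subgroup-by-treatment-by-visit cell terms are the same. A plain difference in Hgb between hyporesponders and others, or a uniform difference between arms, contributes to it. Reported as an interaction p-value, it could suggest a treatment effect that varies across subgroups when it does not. Because it spreads its power over many degrees of freedom, it could also miss an interaction that is present at Week 52. Since the SAP treats non-significance as support for consistency, both errors would matter to the reading.

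**Working it through.** **Design figures first.** Protocol 10.1.1 gives SD 1.5 g/dL, 268 and 134 randomized, and about 10% without Hgb in the evaluation period. That leaves 0.9 x 268 = 241.2 and 0.9 x 134 = 120.6. SE = 1.5 x sqrt(1/241.2 + 1/120.6) = 0.167. Half-width = 1.96 x 0.167 = 0.328, limit = -0.75 + 0.328 = -0.422, and power at a true difference of 0 is 99.4%. The protocol states 0.33, -0.42 and more than 90%, so its figures reproduce. The present point does not depend on them beyond the SD and the roughly 360 evaluable participants.

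**Degrees of freedom.**
- Lone three-way term, hyporesponder: 2 x 2 x 7 = 28 cells, so 27 df.
- Lone three-way term, region: 5 x 2 x 7 = 70 cells, so 69 df.
- Week 52 subgroup-by-treatment contrast: (2-1)(2-1) = 1 df for hyporesponder and (5-1)(2-1) = 4 df for region.

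**Is the fit equivalent?** One simulated dataset (hyporesponder effect -0.6 g/dL, no interaction) was fitted both ways, as a full factorial and with the three-way term alone. Fitted values agreed to 2e-12 and the covariance matrices matched. The Week 52 contrast gave p = 0.01564 from both fits. The true three-way contrast (6 df) gave p = 0.8998 from both. The test of the lone term (27 df) gave p = 0.269. So the fit is the same and the lone-term test addresses a different hypothesis.

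**How far could the lone-term test mislead?** Simulation with no interaction, nominal 10%, 600 runs per scenario.
- From the documents: N about 360, 2:1 allocation, 7 visits, SD 1.5, region, baseline and baseline-by-time terms.
- Assumed: hyporesponder share 15%, within-person correlation 0.5, baseline SD 0.9, baseline slope -0.8, complete data, baseline not centred (no centring is stated).
- Residual SD = sqrt(1.5^2 - (0.8 x 0.9)^2) = 1.32.
- Monte Carlo SE at 10% = sqrt(0.1 x 0.9/600) = 1.2 points.

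| True effects (g/dL) | Lone three-way term | Week 52 contrast |
|---|---|---|
| None | 10.8% | 9.5% |
| Subgroup -0.3 | 24.2% | 11.0% |
| Subgroup -0.6 | 71.8% | 10.5% |
| Subgroup -0.6, correlation 0.7 | 57.7% | 9.2% |
| Subgroup -0.6, correlation 0.3 | 86.0% | 10.5% |
| Subgroup -0.6, 30% hyporesponders | 94.0% | 10.5% |
| Subgroup -1.0 | 99.2% | 10.5% |
| Subgroup -1.0, 30% hyporesponders | 100% | 8.0% |
| Treatment 0.3, uniform | 33.0% | 9.5% |
| Treatment 0.5, uniform | 81.8% | 9.0% |
| Subgroup -0.6, treatment 0.2, drift 0.3 | 83.0% | 10.3% |
| Time drift 0.3 | 10.3% | 10.8% |
| Time drift 0.5 | 12.8% | 10.8% |
| Time drift 1.0 | 19.2% | 11.0% |

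A uniform difference of size 0.3 is within the range that Protocol 10.1.2 considers. Time drift adds little. With baseline-by-time in the model and baseline uncentred, the cell terms are intercepts at a baseline Hgb of 0, far from the 8 to 11.5 g/dL entry range, so differences between visits in those terms are poorly estimated. Power under a true interaction was not simulated. That the lone-term test could miss one follows from its 27 or 69 df, and the dataset above (0.269 against 0.016) shows how far apart the two p-values can be.

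**The case against.** The SAP asks for the right quantity, a subgroup-by-treatment p-value, and nowhere says that it will be the Type 3 F test of the three-way term. With no two-way term in the model, a careful programmer would build a contrast. SAP 7.3.1 already takes the main treatment comparison for this endpoint from LS means at Week 52, and says the subgroup method resembles that of the primary analysis, which has an explicit interaction. Table shells are in a separate document. Moreover, a full factorial would not settle the matter: its subgroup-by-treatment test averages over visits, so a Week 52 contrast would be needed there too. The real gap is the unnamed contrast.

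Most of this stands. A reader might infer that the planned interaction p-value will be wrong; the documents do not support that, because it needs a reporting choice that the SAP does not state. A reader might also infer that time trends alone would produce false interactions. That appears when baseline is left out or centred. With five regions and only a 0.2 g/dL drift (500 runs, SD 1.2), rejection was 42% without baseline but 8% with the SAP's uncentred baseline-by-time term.

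What does not fall away is that the SAP deletes the usual source of this p-value, calls the result equivalent and puts nothing in its place. Its ANCOVA (5.4.2, 7.2.5.1) and Cox (7.3.1, Time to Rescue) subgroup models keep an explicit treatment-by-subgroup term. Section 5.4.2 also sets out the convergence steps for this very MMRM in detail.

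**Conclusion.** The concern holds in conditional form. The equivalence statement is correct for the fit, LS means, within-level differences with their intervals, and any explicit contrast. It is not correct for the test of the remaining term. If that test were reported as the interaction p-value, it would reject about 24% to 72% of the time for subgroup effects of -0.3 to -0.6 g/dL with no interaction (58% to 94% for -0.6 across the assumptions tried) and 33% for a uniform treatment difference of 0.3, against 8% to 11% for the Week 52 contrast. These rates rest on the assumed hyporesponder share, correlation, baseline slope and complete data. For region, only the degrees of freedom are claimed.

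A reader might take this to cast doubt on the trial's main conclusions. It does not. The model serves one secondary endpoint, which the protocol calls exploratory, in two subgroups (SAP Tables 2.030 and 2.031). The primary and principal secondary subgroup analyses use ANCOVA with an explicit interaction term. No non-inferiority or superiority decision depends on this p-value. Severity: minor.

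**What to change.** In SAP 5.4.2, limit the equivalence statement to the model fit, LS means and contrasts built from them. Add that, for the MMRM, the subgroup-by-treatment p-value comes from an explicit Week 52 contrast comparing (daprodustat - rhEPO) between subgroup levels, with 1 df for hyporesponder and 4 df for region, and not from the Type 3 test of the three-way term. The three-way-only parameterization can stay.

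The cost is one sentence and one contrast statement per model (LSMESTIMATE or CONTRAST in the SAS procedure already planned), for both the all-available and the evaluable Hgb versions. No new data are needed and no main analysis changes.
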